#### **Additional Figures:**

Figure 4: System Usability Scale (SUS)

## System Usability Scale (SUS)

Statement:	Rating				
	Strongly	Disagree	Undecided	Agree	Strongly
	disagree				Agree
I think that I would like to use this system					
frequently					
I found the system unnecessarily complex					
I thought the system was easy to use					
I think that I would need the support of a					
technical person to be able to use this system					
I found the various functions in this system were well integrated					
I thought there was too much inconsistency in this system					
I would imagine that most people would learn to use this system very quickly					
I found the system very cumbersome to use					
I felt very confident using the system					
I needed to learn a lot of things before I could					
get going with this system					

## Figure 5: Simulation Effectiveness Tool (SET-M)

#### Simulation Effectiveness Tool - Modified (SET-M)

After completing a simulated clinical experience, please respond to the following statements by circling your response.

PREBRIEFING:	Strongly Agree	Somewhat Agree	Do Not Agree
Prebriefing increased my confidence	3	2	1
Prebriefing was beneficial to my learning.	3	2	1
SCENARIO:			•
I am better prepared to respond to changes in my patient's condition.	3	2	1
I developed a better understanding of the pathophysiology.	3	2	1
I am more confident of my nursing assessment skills.	3	2	1
I felt empowered to make clinical decisions.	3	2	1
I developed a better understanding of medications. (Leave blank if no medications in scenario)	3	2	1
I had the opportunity to practice my clinical decision making skills.	3	2	1
I am more confident in my ability to prioritize care and interventions	3	2	1
I am more confident in communicating with my patient.	3	2	1
I am more confident in my ability to teach patients about their illness and interventions.	3	2	1
I am more confident in my ability to report information to health care team.	3	2	1
I am more confident in providing interventions that foster patient safety.	3	2	1
I am more confident in using evidence-based practice to provide nursing care.	3	2	1
DEBRIEFING:			
Debriefing contributed to my learning.	3	2	1
Debriefing allowed me to verbalize my feelings before focusing on the scenario	3	2	1
Debriefing was valuable in helping me improve my clinical judgment.	3	2	1
Debriefing provided opportunities to self-reflect on my performance during simulation.	3	2	1
Debriefing was a constructive evaluation of the simulation.	3	2	1
What else would you like to say about today's simulated clinical experience?			

Figure 6: Anaphylaxis Checklist of Core Decision Making Steps

History (10 points)  Symptom duration [1]  Inciting factors [2]  Airway management questions (i.e. sob) [2]  Other symptoms [1]  Past medical history [1]  Medications [1]  Allergies [2]  Physical (15 points)  Airway assessment [3]  Breath sounds [3]  Pulse oximetry [3]  Respiratory rate [2]  Cardiac exam [1]  Blood pressure [1]  Pulse [1]  Extremity/skin [1]

 
□ Inciting factors [2]
 
□ Airway management questions (i.e. sob) [2]
 
□ Other symptoms [1]
 
□ Past medical history [1]
 
□ Medications [1]
 
□ Allergies [2]
 
Physical (15 points)
 
□ Airway assessment [3]
 
□ Breath sounds [3]
 
□ Pulse oximetry [3]
 
□ Respiratory rate [2]
 
□ Cardiac exam [1]
 
□ Blood pressure [1]
 
□ Pulse [1]
 

 
□ Airway management questions (i.e. sob) [2]
 
□ Other symptoms [1]
 
□ Past medical history [1]
 
□ Medications [1]
 
□ Allergies [2]
 
Physical (15 points)
 
□ Airway assessment [3]
 
□ Breath sounds [3]
 
□ Pulse oximetry [3]
 
□ Respiratory rate [2]
 
□ Cardiac exam [1]
 
□ Blood pressure [1]
 
□ Pulse [1]
 

 
□ Other symptoms [1]
 
□ Past medical history [1]
 
□ Medications [1]
 
□ Allergies [2]
 
Physical (15 points)
 
□ Airway assessment [3]
 
□ Breath sounds [3]
 
□ Pulse oximetry [3]
 
□ Respiratory rate [2]
 
□ Cardiac exam [1]
 
□ Blood pressure [1]
 
□ Pulse [1]
 

 
□ Past medical history [1]
 
□ Medications [1]
 
□ Allergies [2]
 
Physical (15 points)
 
□ Airway assessment [3]
 
□ Breath sounds [3]
 
□ Pulse oximetry [3]
 
□ Respiratory rate [2]
 
□ Cardiac exam [1]
 
□ Blood pressure [1]
 
□ Pulse [1]
 

 
□ Medications [1]
 
□ Allergies [2]
 
Physical (15 points)
 
□ Airway assessment [3]
 
□ Breath sounds [3]
 
□ Pulse oximetry [3]
 
□ Respiratory rate [2]
 
□ Cardiac exam [1]
 
□ Blood pressure [1]
 
□ Pulse [1]
 

□ Allergies [2]  Physical (15 points) □ Airway assessment [3] □ Breath sounds [3] □ Pulse oximetry [3] □ Respiratory rate [2] □ Cardiac exam [1] □ Blood pressure [1] □ Pulse [1]
Physical (15 points)  Airway assessment [3]  Breath sounds [3]  Pulse oximetry [3]  Respiratory rate [2]  Cardiac exam [1]  Blood pressure [1]  Pulse [1]

 
□ Airway assessment [3]
 
□ Breath sounds [3]
 
□ Pulse oximetry [3]
 
□ Respiratory rate [2]
 
□ Cardiac exam [1]
 
□ Blood pressure [1]
 
□ Pulse [1]
 


 
□ Breath sounds [3]
 
□ Pulse oximetry [3]
 
□ Respiratory rate [2]
 
□ Cardiac exam [1]
 
□ Blood pressure [1]
 
□ Pulse [1]
 

□ Pulse oximetry [3] □ Respiratory rate [2] □ Cardiac exam [1] □ Blood pressure [1] □ Pulse [1]
□ Respiratory rate [2] □ Cardiac exam [1] □ Blood pressure [1] □ Pulse [1]
☐ Cardiac exam [1] ☐ Blood pressure [1] ☐ Pulse [1]
☐ Blood pressure [1] ☐ Pulse [1]
□ Pulse [1]
☐ Extremitv/skin [1]
Diagnostic evaluation (0 points)
Management (20 points)
☐ Epinephrine [3]
Oxygen (mask or intubation) [3]
☐ H1 blocker [2]
☐ H2 blocker [1]
☐ Steroids [2]
□ IV with fluids [3]
☐ Monitor [1]
☐ Albuterol nebs [1]
☐ Observation [1]
□ Notify PMD [1]
☐ Bracelet [1] ☐ Epi-pen Rx [1]

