## Statistical Analysis:

SUS and mixed reality specific questionnaire results will be compiled in aggregate and descriptive statistics will be presented as frequencies. For the items of the SUS, the score will be calculated using Brooke's standard scoring method.

Second Research Question (Study Phase II): Evaluation of the novel mixed reality based anaphylaxis curriculum as a teaching and assessment tool

In the second study phase the HoloSIM platform will be incorporated into a novel anaphylaxis education and assessment curriculum and evaluated by randomized control trial. The primary outcome will be the impact on technical and nontechnical skill

acquisition as assessed by performance checklist; secondary outcomes include the scenario related declarative knowledge assessed by multiple choice quiz, as well as learner perceptions of the mixed reality assessment tool as measured by questionnaire. The nature, timing, and validity of these measurement tools is outlined below.

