## Recruitment and study workflow:

Acute care residents will be recruited and consented for a randomized control trial via email invitation and REDCap software. Participants will be asked to complete baseline measurements of simulation, anaphylaxis management, and immersive device (virtual reality or mixed reality) experience.

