### Study Conduct and Data Collection:

Group A (Intervention). Participants randomized to Group A will arrive on day 0 to be given an orientation to the immersive HoloSIM platform. When they feel accustomed to its technical aspects an anaphylaxis management scenario will be initiated.

Group B (Control). Participants randomized to Group B will be assigned to mannequin-based scenario practice, which is the current gold standard in medical education and

assessment. Similar to the HoloSIM group, participants will arrive on day 0 to be given an orientation to the mannequin-based simulation environment so that they feel accustomed to its technical aspects. The anaphylaxis management scenario will match the HoloSIM environment and sequence of events.

All participants will receive learning objectives and a handout with educational content previously developed by a panel of allergists and be asked to review it approximately 48 hours prior to the intervention simulation session.

Participants will have access to the same handouts provided at the time on enrollment for debriefing after each practice session, as well as an instructor led debrief. All participants will then complete a validated assessment of learning satisfaction tool, the Modified Simulation Effectiveness Tool (SET-M, see Supplementary Figure 5) ; if HoloSIM is utilized, participants will complete usability questionnaires as in the first study phase.

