## Statistical analysis:

Demographic characteristics of participants will be summarized with appropriate measures of central tendency and dispersion (count/percent for categorical data). The mean checklist scores in each group will be presented as mean/standard deviation and inferential testing will be done with the t-test. The inter-assessor agreement will be measured using the interclass correlation coefficient (ICC).

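### Two of the 12 scenario items on the SET-M given to physician residents are worded for nurses; adapt the wording before use and qualify the claim that the form is validated (minor).

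*Protocol*

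**What the plan says.** The Phase II population is set under Recruitment and study workflow: "Acute care residents will be recruited and consented for a randomized control trial via email invitation and REDCap software". Randomisation is stratified by specialty, and the specialties named for Phase I are anesthesiology, internal medicine, critical care and emergency medicine. No nurses are recruited.

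Under Study Conduct and Data Collection, after the practice session and debrief, "All participants will then complete a validated assessment of learning satisfaction tool, the Modified Simulation Effectiveness Tool", with a pointer to Figure 5. Usability questionnaires are added only for those who used HoloSIM.

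Figure 5 prints the form: 2 prebriefing, 12 scenario and 5 debriefing items, each rated 1 to 3. Two scenario items read "I am more confident of my nursing assessment skills" and "I am more confident in using evidence-based practice to provide nursing care". The only item with an instruction to leave it blank is the one on medications.

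The introduction to the Second Research Question lists among the secondary outcomes "learner perceptions of the mixed reality assessment tool as measured by questionnaire". It does not name the SET-M. The Phase II analysis section says: "The mean checklist scores in each group will be presented as mean/standard deviation and inferential testing will be done with the t-test". It states no scoring rule or arm comparison for the SET-M.

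**The concern.** A resident in anesthesiology or emergency medicine who is asked about nursing assessment or nursing care has three options: read the item as referring to their own assessment and care, give the lowest rating because the item does not describe them, or skip it. Different residents will choose differently, and the form gives no guidance. The spread this produces has nothing to do with the training they received.

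The word validated also claims more than the protocol shows. The introduction to Phase II promises an account of the validity of the measurement tools. For the SET-M the account consists of that one word and a reference, which the literature list places in a nursing education journal. Nothing in the protocol speaks to validity in physicians.

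At stake is the quality of a secondary questionnaire. Among the post-session questionnaires it is the only one given in both arms, so any comparison of how the two groups perceived their session would rest on it. An analysis plan can decide how blanks are scored, but it cannot reword an item that has already been answered.

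**Working it through.** The protocol gives no score, standard deviation, effect size or power for the SET-M, so there is no figure of its own to reproduce. The check is a count from Figure 5 followed by a bounded illustration.

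**Count**
- Items: 2 + 12 + 5 = 19. Nursing-worded items: 2, both in the scenario block.
- Share of scenario items: 2/12 = 16.7%. Share of all items: 2/19 = 10.5%.
- Each item spans 2 points (1 to 3), so the two items carry 4 of the 24 points of scenario range and 4 of the 38 points of whole-form range (19 to 57, if items are simply summed, which the protocol does not state).

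**Raw arm difference**

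Assume every item would shift by *d* between arms if properly worded, and that the two nursing items shift by nothing. The mean over *k* items then shifts by (*k* − 2)*d*/*k* instead of *d*:
- Scenario items: 10/12 = 0.833, a loss of 16.7%.
- Whole form: 17/19 = 0.895, a loss of 10.5%.

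If the two items respond in part, the loss is smaller.

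**Standardised arm difference**

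Further assume items of equal variance with common correlation ρ between 0.3 and 0.7, and write *g* = *k* − 2. With all items working, the standardised difference is proportional to *k*/√(*k* + *k*(*k* − 1)ρ).

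1. If the two items are independent noise, it becomes *g*/√(*g* + *g*(*g* − 1)ρ + 2). For *k* = 12 and ρ = 0.3 the two values are 12/√51.6 = 1.671 and 10/√39 = 1.601, a ratio of 0.959.
2. If the two items correlate with the rest like any other item but carry no arm effect, the denominator is unchanged and the ratio is *g*/*k*.

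| Items | ρ | Ratio, independent noise | Ratio, correlated, no arm effect |
|---|---|---|---|
| 12 (scenario) | 0.3 | 0.959 | 0.833 |
| 12 (scenario) | 0.5 | 0.975 | 0.833 |
| 12 (scenario) | 0.7 | 0.983 | 0.833 |
| 19 (whole form) | 0.3 | 0.984 | 0.895 |
| 19 (whole form) | 0.5 | 0.991 | 0.895 |
| 19 (whole form) | 0.7 | 0.994 | 0.895 |

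The loss in standardised difference is therefore about 2 to 4% (scenario) or 1 to 2% (whole form) under independent noise, and 16.7% or 10.5% in the worse case.

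**Bias**

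Suppose residents in both arms mark 1 instead of 3 on both items. Each arm's total falls by 2 × 2 = 4 points, and the difference between arms changes by 4 − 4 = 0.

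**The case against.** The strongest reply is that this is a wording mismatch on an appendix form, with no analysis attached to it. The Phase II analysis section plans a t-test for checklist scores only, the secondary outcome on learner perceptions does not name the SET-M, and the conduct section describes the form as measuring satisfaction with learning. All of that is correct, and it limits the point to data quality.

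Three stronger readings are tempting, and the protocol does not support them.

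- A reader might infer that the two items cannot be validly answered. That does not follow: a resident can sensibly read them as being about their own assessment and care. What the page shows is ambiguity and possible blanks.
- A reader might infer that a planned arm comparison is spoiled, or pushed towards a finding of comparability. No SET-M comparison is stated. The non-inferiority margin belongs to the 45-point checklist, and both randomised groups receive the same form, so a uniform shift cancels.
- A reader might infer that the prebriefing and debriefing items cannot reflect the modality either, and that only the scenario items should be compared. The orientation before the scenario differs by arm, and debriefing ratings may reflect the scenario just run. How the form is scored is a matter for an analysis plan.

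What remains is that the protocol fixes the instrument, prints its wording, gives it to physicians and calls it validated without qualification.

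**Conclusion.** The point holds as a minor one. Two of 12 scenario items (2 of 19 overall) name a profession that no Phase II participant belongs to, and the protocol mentions no adaptation. The consequence is avoidable ambiguity, noise or missing answers in a questionnaire collected in both arms.

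The figures of 16.7% (scenario) and 10.5% (whole form) for dilution of a raw arm difference assume that the two items carry no arm effect and that the other items shift equally. Under independent noise the standardised loss is only a few per cent. Treating the SET-M as a measure for the learner-perception outcome is a reasonable inference, not something the protocol states. No directional bias is evident, and the checklist outcome, its margin and the sample size are unaffected.

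**What to change.** Before the first participant completes the form, change *nursing assessment skills* to *clinical assessment skills* and *nursing care* to *patient care* in Figure 5, identically in both arms. In Study Conduct and Data Collection, describe the form as *SET-M, adapted for physicians* in place of the unqualified claim of validation.

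The cost is two changes of wording and one sentence. The form then departs slightly from the printed wording, and the label declares this.
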